**Figure 1 Overall study design**

OS Overall survival; PD-L1 Programmed cell death ligand 1; PS Eastern Cooperative Oncology Group performance status; SCCHN Squamous cell cancer of the head and neck; SoC Standard of Care.

**Figure 2 Study flow chart-treatment period**

[figure not shown]

a Informed consent of study procedures and tumor biopsy sample may be obtained prior to the 28-day screening window, if necessary, in order to permit tumor biopsy sample acquisition and analysis prior to randomization

b Disease progression requires confirmation for patients receiving IMT. Disease progression in patients in the SoC arm should be confirmed if clinically feasible (see Section 5.1 of the CSP for more information).

- c Patients in the MEDI4736 + tremelimumab combination therapy arm who are eligible for retreatment will be treated according to Figure 3
- d This refers to Table 3 in the CSP
- e This refers to Table 4 in the CSP
- IMT Immunomodulatory therapy; PD Progressive disease; RECIST 1.1 Response Evaluation Criteria in Solid Tumors version 1.1.

**Figure 3 Study flow chart - optional retreatment for MEDI4736 + tremelimumab arm**

- a With or Without confirmation
- b Before restarting MEDI4736 + tremelimumab combination therapy, the Investigator should ensure that the patient does not have any significant, unacceptable, or irreversible toxicities that indicate that continuing treatment will not further benefit the patient, and that the patient still meets all of the inclusion criteria and none of the exclusion criteria for this study including re-consenting to restart treatment. To restart study treatment, the patient must not have received an intervening cancer therapy post study treatment discontinuation. Patients should have a baseline tumor assessment within 28 days of restarting study treatment; all further scans should occur q8w until PD (relative to the date of restarting study treatment).
- c This refers to Table 2 in the CSP. PK, ADA, and MDSC assessments do not need to be collected during retreatment.
- d This refers to Table 4 in the CSP
- ADA Anti-drug antibody; MDSC Myleoid-derived suppressor cell; PK Pharmacokinetics; q8w Every 8 weeks; RECIST 1.1 Response Evaluation Criteria in Solid Tumors version 1.1.

### 1.3 Number of subjects

The sample size for this study was selected to be consistent with the research hypothesis as described in Section 8.5 of the Clinical Study Protocol (CSP).

The study will enroll approximately 1016 patients in order to randomize 760 eligible patients in a 2:1:1 ratio (380:190:190 patients) to MEDI4736 + tremelimumab combination therapy, MEDI4736 monotherapy, or SoC respectively.

The study was originally sized to characterize the OS benefit of MEDI4736 + tremelimumab combination therapy versus SoC in all-comers (i.e., regardless of PD-L1 tumor expression status) and in PD-L1 TC/IC subgroup population. The sizing assumes a 3-month delay in separation of the OS curves between each arm, hence the use of average HRs.

With amendment 11 (CSP version 12) the primary objective was changed to characterize the OS benefit of MEDI4736 monotherapy versus SoC in the PD-L1 TC/IC high subgroup. Due to this change the primary analysis of OS will be performed when approximately 147 death events have occurred in approximately 172 patients (85% maturity) across the MEDI4736 monotherapy and SoC treatment groups in the PD-L1 TC/IC high subgroup population. The number of patients (172) assumes that 45% of patients randomized are within this subgroup. No interim efficacy analyses will be performed in this study.

If superiority over SoC is found, a hierarchical multiple testing procedure (MTP) will be employed to strongly control for the overall type I error at the 5% alpha level (two-sided), as shown in Section 4, Figure 4.

#### **MEDI4736 Monotherapy versus SoC in the PD-L1 TC/IC high subgroup (OS)**

If OS at 24 months in the PD-L1 TC/IC high subgroup was 30% with MEDI4736 monotherapy and 12% with SoC (with a 10.1-month median OS), and assuming the true average OS HR is 0.59; the trial will have approximately 90% power to demonstrate statistical significance at the 5% level (using a 2-sided test) for the comparison of MEDI4736 monotherapy versus SoC in the PD-L1 TC/IC high subgroup, with approximately 147 events. With a 17-month recruitment period and a minimum follow-up period of 23.6 months from “last patient in” assumed, it is anticipated that the analysis will be performed approximately 40.6 months after the first patient has been recruited.

#### **MEDI4736 Monotherapy versus SoC in the low risk of EM subgroup (OS)**

Assuming approximately 80% of patients are in the low risk of EM subgroup and assuming the true average OS HR is 0.70, the trial will have approximately 81% power to demonstrate statistical significance at the 5% level (using a 2-sided test) for the comparison of MEDI4736 monotherapy versus SoC in the low risk of EM subgroup, with approximately 254 events.

#### **MEDI4736 Monotherapy versus SoC in the ctDNA TMB high ( $\geq 16$ mut/Mb) subgroup (OS)**

Assuming approximately 16% of patients are in the ctDNA TMB high ( $\geq 16$  mut/Mb) subgroup and assuming the true OS HR is 0.40, the trial will have approximately 82% power to demonstrate statistical significance at the 5% level (using a 2-sided test) for the comparison of MEDI4736 monotherapy versus SoC in the ctDNA TMB high ( $\geq 16$  mut/Mb) subgroup, with approximately 48 events.

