#### **MEDI4736 + tremelimumab combination therapy versus SoC in the ctDNA TMB high ( $\geq 16$ mut/Mb) subgroup (OS)**

Assuming the true OS HR is 0.40, the trial will have approximately 92% power to demonstrate statistical significance at the 5% level (using a 2-sided test) for the comparison of MEDI4736 + tremelimumab combination therapy versus SoC in the ctDNA TMB high ( $\geq 16$  mut/Mb) subgroup, with approximately 68 events.

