**Table 5 Summary of Statistical Assumptions and Calculations**

	N ratio	Overall HR	Landmarks at 24 months	Events (maturity)	Power	Critical values HR (landmarks)
Primary Objectives						
OS: Mono versus SoC; PD-L1 TC/IC high subgroup	86:86	0.59	30% vs 12%	147 (85%)	90%	0.72 (22%)
Secondary objectives:						
OS: Mono versus SoC; low risk of EM subgroup	152:152	0.70	24% vs 12%	254 (84%)	81%	0.78 (19%)
OS: Mono versus SoC; ctDNA TMB high ( $\geq 16$ mut/Mb) subgroup	30:30	0.40	43% vs 12%	48 (80%)	88%	0.56 (29%)
OS: Combo versus SoC; ctDNA TMB high ( $\geq 16$ mut/Mb) subgroup	60:30	0.40	43% vs 12%	68 (76%)	96%	0.62 (26%)
OS: Mono versus SoC; all-comers	190:190	0.70	24% vs 12%	336 (88%)	91%	0.81 (18%)
OS: Combo versus SoC; all-comers	380:190	0.70	24% vs 12%	495 (87%)	97%	0.83 (17%)

Note: The sample size estimates in the PD-L1 TC/IC high subgroup comparisons assume that 45% of the patients enrolled are within this subgroup. The sample size estimates in the low risk of EM subgroup assume that 80% of the patients randomized are within this subgroup. The sample size estimates in the ctDNA TMB high ( $\geq 16$  mut/Mb) subgroup assume that 16% of the patients randomized are within this subgroup. A 3-month delayed effect is assumed for all hypotheses except for ctDNA TMB high.

Combo MEDI4736 + tremelimumab combination therapy; HR Hazard ratio; IC tumor-associated immune cells; Mono MEDI4736 monotherapy; OS Overall survival; SoC Standard of Care; PD-L1 Programmed cell death ligand 1; PFS Progression-free survival; TC Tumor cells; TMB Tumor Mutational Burden.

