### Multiple testing strategy

In order to strongly control the type I error at 5% 2-sided, a multiple testing procedure (MTP) will be used across the primary endpoint (OS), treatment regimens (MEDI4736 monotherapy, MEDI4736 + tremelimumab, and SoC), and across the analysis populations (PD-L1 TC/IC

[figure not shown]
high subgroup, low risk of EM subgroup, ctDNA TMB high ( $\geq 16$  mut/Mb) subgroup and all-comers). If the highest-level hypothesis in the MTP is statistically significant, the next hypothesis in the hierarchy will then be tested as shown in [Figure 4](#)).

Hypotheses will be tested using a hierarchical multiple testing procedure to control for the overall type I error at the 0.05 level (two-sided). With this approach, hypotheses will be tested in a predefined order (sequentially rejective manner at  $\alpha=0.05$ ) as outline in [Figure 4](#).

Hypotheses in the hierarchy will be to test MEDI4736 monotherapy versus SoC in the PD-L1 TC/IC high subgroup population followed by MEDI4736 monotherapy versus SoC in the low risk of EM subgroup population, then MEDI4736 monotherapy versus SoC in the ctDNA TMB high ( $\geq 16$  mut/Mb) subgroup, then MEDI4736 + tremelimumab combination therapy versus SoC in the ctDNA TMB high ( $\geq 16$  mut/Mb) subgroup, then MEDI4736 monotherapy versus SoC in all-comers and finally MEDI4736 + tremelimumab combination therapy versus SoC in all-comers. All tests will be at the two-sided 5% alpha level and the procedure will stop at the first failure to find statistically significant evidence of superiority or if tests of all hypotheses show statistically significant evidence of superiority over SoC.

Note: the comparisons of MEDI4736 + tremelimumab combination therapy versus MEDI4736 monotherapy and the comparison of MEDI4736 + tremelimumab combination therapy versus SoC (in the PD-L1 TC/IC high subgroup and low risk of EM subgroup) will not be included in the MTP, and therefore will not be conducted under strict alpha control.

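### SAP Section 1.3 gives 82% and 92% power for the two ctDNA TMB-high OS tests, but Table 5 gives 88% and 96% from the same inputs; the text figures do not reproduce

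*SAP*

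**What the plan says.** SAP Section 1.3 has a short paragraph on each hypothesis in the testing hierarchy.

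- **Monotherapy versus SoC, ctDNA TMB high:** for a true HR of 0.40, "the trial will have approximately 82% power to demonstrate statistical significance at the 5% level", "with approximately 48 events".
- **Combination versus SoC, ctDNA TMB high:** "Assuming the true OS HR is 0.40, the trial will have approximately 92% power", "with approximately 68 events".

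Section 1.3 then introduces Table 5 as a summary of these assumptions and calculations. The two TMB-high rows of Table 5 read:

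| Comparison | N | HR | 24-month OS | Events | Power | Critical HR |
|---|---|---|---|---|---|---|
| Mono vs SoC | 30:30 | 0.40 | 43% vs 12% | 48 (80%) | 88% | 0.56 |
| Combo vs SoC | 60:30 | 0.40 | 43% vs 12% | 68 (76%) | 96% | 0.62 |

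The note to Table 5 adds: "A 3-month delayed effect is assumed for all hypotheses except for ctDNA TMB high". On the significance level, the multiple testing strategy in SAP Section 4 says: "All tests will be at the two-sided 5% alpha level".

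**The concern.** Text and table use the same hazard ratio, events and significance level for each comparison, yet report different power. Because the table is offered as a summary of the text, it cannot be read as a separate scenario. Only these two hypotheses are affected: for the other four, text and table agree (90%, 81%, 91% and 97%).

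These are levels 3 and 4 of the hierarchy, tested under strict alpha control, and a failure at either level stops testing before the all-comers hypotheses. Anyone interpreting a non-significant TMB-high result will want the planned type II error, and the SAP gives two values for each test: 18% or 12% for monotherapy, and 8% or 4% for the combination. The protocol does not settle the matter, because its Table 11 (Section 8.2) covers only the first two levels.

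**Working it through.** **Inputs.** Two-sided alpha 0.05 (SAP Section 4); HR 0.40 and 48 or 68 events (SAP Section 1.3 text and Table 5); allocation 30:30 and 60:30 (Table 5); no delayed effect for TMB high (note to Table 5). The landmarks fit a proportional effect: ln 0.43 / ln 0.12 = 0.398. The SAP names no power formula, so several were tried.

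**1. Schoenfeld formula.** Power = Φ(|ln HR| × √(D × p × (1 − p)) − 1.96), where D is the number of events and p the allocation fraction; |ln 0.40| = 0.916.

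- Mono: Φ(0.916 × √(48 × 0.25) − 1.96) = **88.8%**. Table 5 says 88%, the text 82%.
- Combo: Φ(0.916 × √(68 × 2/9) − 1.96) = **94.5%**. Table 5 says 96%, the text 92%.

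The same formula comes within 1 point of the SAP's figure for the other four hypotheses:

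| Hypothesis | Events, HR | SAP | Recomputed |
|---|---|---|---|
| Mono, PD-L1 TC/IC high | 147, 0.59 | 90% | 89.2% |
| Mono, low risk of EM | 254, 0.70 | 81% | 81.1% |
| Mono, all-comers | 336, 0.70 | 91% | 90.5% |
| Combo, all-comers (2:1) | 495, 0.70 | 97% | 96.3% |

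**2. Expected split of events.** With HR 0.40, SoC patients die sooner, so events do not divide in the ratio of patients. *Assume* about 95% of SoC patients have died at analysis (28.5 of 30; not stated in the SAP). Then SE = √(1/d₁ + 1/d₀).

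- Mono: d₁ = 48 − 28.5 = 19.5; SE = 0.294; power = Φ(0.916/0.294 − 1.96) = **87.7%**; critical HR = exp(−1.96 × 0.294) = 0.562.
- Combo: d₁ = 68 − 28.5 = 39.5; SE = 0.246; power = **96.1%**; critical HR = 0.618.

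These match Table 5's 88% with 0.56 and 96% with 0.62.

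**3. Power implied by Table 5's critical hazard ratios.** This needs no assumption about the event split. The critical HR fixes the standard error: SE = |ln HR_crit| / 1.96.

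- 0.56: SE = 0.580/1.96 = 0.296; power = Φ(0.916/0.296 − 1.96) ≈ 87%. Values that round to 0.56 give 86.2–88.2%.
- 0.62: SE = 0.478/1.96 = 0.244; power ≈ 96%. Values that round to 0.62 give 95.9–96.9%.

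Power of 82% would need a critical HR near 0.535, and 92% one near 0.586. Neither rounds to the printed value.

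**4. Other routes to 82% and 92%.**

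| Method | Mono (text 82%) | Combo (text 92%) |
|---|---|---|
| Freedman | 84.4% | 97.3% (2:1); 83.0% (ratio reversed); 94.2% (1:1 form) |
| One-sided 5% | 93.7% | 97.2% |
| Simulated unstratified log-rank, 17-month accrual, 20,000 runs | 87.2–87.7% | 95.5–95.8% |
| Same simulation with a 3-month delay | 65–72% | 78–85% |

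None is within 2 points of the text figure. The nearest miss by 2.4 points (mono) and 2.2 points (combo). At HR 0.40, 82% corresponds to about 39 events and 92% to about 61 events at 2:1, not 48 and 68. With the stated events, the hazard ratios would have to be about 0.44 and 0.42.

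**The case against.** The strongest counter-argument is that the planned OS test is a stratified log-rank test (SAP Section 4.2.1). PD-L1 status, smoking history and tumor location with HPV status can form up to 12 strata, spread over only 60 or 90 patients. Stratifying that finely costs power. Simulations of the stratified test (4,000 runs each) gave 80–82% and 93–94.5% with four to six equal strata, and 80% and 92.5% with 12 heavily skewed strata. With 12 equal strata the figures fell to 71% and 88%. The text figures could therefore come from a different calculation rather than a slip, and raising them to Table 5's values could overstate the power of the test actually used.

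Part of this stands: power for the stratified test may well be below 88% and 96%. As an explanation of the text it is weak. The stratum prevalences in those simulations are assumed, not taken from the documents. Section 1.3 does not mention stratification in its power statements, and for the other four hypotheses text and table agree on figures that the unstratified formula reproduces. Even if it were the explanation, the table would not be summarising the text.

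Two smaller points are fair. Schoenfeld with the 2:1 patient split gives 94.5% for the combination, and reaching 96% requires an assumed event split, although Table 5's critical HR of 0.62 supports 96% without one. The practical reach is also limited: these tests occur only if the preceding levels succeed, and neither power figure sets the sample size, event trigger, alpha, test order or analysis method.

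**Conclusion.** The concern holds. The SAP states two different powers for each TMB-high hypothesis from identical inputs, and the text is the side that does not fit. Recomputed power is 87.7–88.8% for monotherapy against 82% in the text (about 6–7 points low), and 94.5–96.1% for the combination against 92% (about 2.5–4 points low). Table 5's powers agree with its own event counts and critical hazard ratios.

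This rests on proportional hazards with HR 0.40, two-sided 5%, and an unstratified calculation, the convention that reproduces the other four powers. The upper figure for the combination also assumes about 95% SoC maturity. The contradiction itself depends on no formula. It should be corrected because it concerns formally tested hypotheses, but it does not touch the primary analysis or control of type I error.

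**What to change.** In SAP Section 1.3, change 82% to 88% for monotherapy versus SoC and 92% to 96% for combination versus SoC in the TMB-high subgroup, so that the text agrees with Table 5. A sentence naming the power method and the assumed event split would let a reader reproduce both figures.

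If the sponsor intended 82% and 92% as power for the stratified test, or wishes to restate power on that basis, the assumed strata should be given and text and table changed together. The cost is two numbers in the SAP; no analysis, sample size or protocol text changes.

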#### **MEDI4736 + tremelimumab combination therapy versus SoC in the ctDNA TMB high ( $\geq 16$ mut/Mb) subgroup (OS)**

Assuming the true OS HR is 0.40, the trial will have approximately 92% power to demonstrate statistical significance at the 5% level (using a 2-sided test) for the comparison of MEDI4736 + tremelimumab combination therapy versus SoC in the ctDNA TMB high ( $\geq 16$  mut/Mb) subgroup, with approximately 68 events.

### **MEDI4736 monotherapy versus SoC in all-comers (OS)**

If OS at 24 months in the all-comers population was 24% with MEDI4736 monotherapy and 12% with SoC (with a 10.1-month median) and assuming the true average OS HR is 0.70, the trial will have approximately 91% power to demonstrate statistical significance at the 5% level (using a 2-sided test) for the comparison of MEDI4736 monotherapy versus SoC in all-comers, with approximately 336 events. .

### **MEDI4736 + tremelimumab combination therapy versus SoC-all comers (OS)**

With approximately 570 patients randomized across the MEDI4736 + tremelimumab combination therapy and SoC treatment groups and a true average OS HR of 0.70, an estimated 495 death events (87% maturity) are expected to have occurred at 40.6 months from “first patient in,” providing 97% power to demonstrate statistical significance at the 5% level (using a 2-sided test), for the comparison of MEDI4736 + tremelimumab combination therapy versus SoC in all-comers.

[Table 5](#) provides a summary of these statistical assumptions and calculations.

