8.2 Sample size estimate

The study will enroll approximately 1016 patients in order to randomize 760 eligible patients in a 2:1:1 ratio (380:190:190 patients) to MEDI4736 + tremelimumab combination therapy, MEDI4736 monotherapy, or SoC. The study was originally sized to characterize the OS benefit of MEDI4736 + tremelimumab combination therapy versus SoC in the all-comers population. The sizing assumes a 3-month delay in separation of the OS curves between each arm, hence the use of average HRs.

The primary analysis of OS will be performed when approximately 147 death events have occurred in approximately 172 patients (85% maturity) across the MEDI4736 monotherapy and SoC treatment groups in the PD-L1 TC/IC high subgroup, assuming that

45% of the patients randomized are within this subgroup. No interim efficacy analyses will be performed in this study.

If OS at 24 months in the PD-L1 TC/IC high subgroup was 30% with MEDI4736 monotherapy and 12% with SoC (with a 10.1-month median OS), and assuming the true average OS HR is 0.59, the trial will have approximately 90% power to demonstrate statistical significance at the 5% level (using a 2-sided test) for the comparison of MEDI4736 monotherapy versus SoC in the PD-L1 TC/IC high subgroup, with the smallest treatment difference that could be statistically significant being an average HR of 0.72. With a 17-month recruitment period and a minimum follow-up period of 23.6 months from “last patient in” assumed, it is anticipated that the analysis will be performed approximately 40.6 months after the first patient has been recruited.

Table 11 provides a summary of the statistical assumptions for the first two levels of the MTP.

Table 11 Summary of statistical assumptions

	N ratio	Overall HR	Landmarks at 24 months	Events (maturity)	Power	Critical values HR (landmarks)
Primary objective						
OS: Mono versus SoC; PD-L1 TC/IC high subgroup	86:86	0.59	30% vs 12%	147 (85%)	90%	0.72 (22%)
Secondary objectives:						
OS: Mono versus SoC; low risk of EM subgroup	152:152	0.70	24% vs 12%	254 (84%)	81%	0.78 (19%)

Note: The sample size estimates in the PD-L1 TC/IC high subgroup comparisons assume that 45% of the patients randomized are within this subgroup; The sample size estimate in the low risk of EM subgroup assume that 80% of the patients randomized are within this subgroup.

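### SAP 1.3 and Table 5 give stand-alone powers for levels 2-6 as power to show significance, but the fixed sequence caps any formal claim from level 2 on at 81%, and level 6 is nearer 66-70% than 97%

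*SAP*

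**What the plan says.** SAP section 4 (Multiple testing strategy) sets the rule: "All tests will be at the two-sided 5% alpha level and the procedure will stop at the first failure". The order is monotherapy versus SoC in PD-L1 TC/IC high, in low risk of early mortality (EM), and in ctDNA TMB high; then combination versus SoC in TMB high; then monotherapy versus SoC in all-comers; "and finally MEDI4736 + tremelimumab combination therapy versus SoC in all-comers". The Protocol synopsis and Protocol 8.5 describe the same sequence.

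SAP 1.3 mentions the hierarchical procedure and then gives a paragraph of power for each level:

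- Level 1: "assuming the true average OS HR is 0.59; the trial will have approximately 90% power".
- Level 2: "the trial will have approximately 81% power to demonstrate statistical significance at the 5% level".
- Levels 3 and 4: 82% and 92% in the prose, but 88% and 96% in Table 5.
- Level 5: "the trial will have approximately 91% power to demonstrate statistical significance at the 5% level".
- Level 6: "providing 97% power to demonstrate statistical significance at the 5% level (using a 2-sided test".

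Protocol 8.2 goes less far down the list: "Table 11 provides a summary of the statistical assumptions for the first two levels of the MTP". Neither document says that the figures treat each test as if it stood alone, and neither gives a power that allows for the stopping rule.

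**The concern.** In a fixed sequence the probability of declaring level k significant is the probability that levels 1 to k all succeed. That probability cannot rise down the list. The printed powers do rise, from 81% at level 2 to 97% at level 6. Read as the chance of a formal claim, which is how the wording invites them to be read, the figures after level 2 contradict the testing rule.

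SAP 1.3 and Table 5 are the only place where a reader can judge whether the trial can support the TMB, all-comers and combination claims. Taken at face value, those claims look more secure than the primary one.

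**Working it through.** **Inputs.** Deaths, hazard ratios and powers come from SAP 1.3 and Table 5. Allocation is 2:1:1 combination:monotherapy:SoC. Subgroup prevalences (Table 5 note) are 45% PD-L1 high, 80% low risk of EM and 16% TMB high.

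**Step 1: reproduce the stated powers.** Schoenfeld: power = Φ(|ln HR| × √(d·p(1−p)) − 1.960), with d deaths, p = 1/2 for monotherapy versus SoC and p = 1/3 (SoC share) for combination versus SoC. For level 6: 0.3567 × √(495 × 1/3 × 2/3) − 1.960 = 0.3567 × 10.488 − 1.960 = 1.781, and Φ(1.781) = 96.3%.

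| Level | Deaths | HR | Schoenfeld | Table 5 | Prose |
|---|---|---|---|---|---|
| 1 | 147 | 0.59 | 89.2% | 90% | 90% |
| 2 | 254 | 0.70 | 81.1% | 81% | 81% |
| 3 | 48 | 0.40 | 88.8% | 88% | 82% |
| 4 | 68 | 0.40 | 94.5% | 96% | 92% |
| 5 | 336 | 0.70 | 90.5% | 91% | 91% |
| 6 | 495 | 0.70 | 96.3% | 97% | 97% |

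Every Table 5 figure agrees within 2 points, so these are single-test powers. The prose 82% and 92% are not reproduced.

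**Step 2: ceiling, with no modelling.** P(claim at level k) ≤ the smallest stand-alone power among levels 1 to k. That is 90% at level 1 and min(90, 81, ...) = 81% from level 2 on. The matching floor at level 6 with Table 5 powers is 1 − (0.10 + 0.19 + 0.12 + 0.04 + 0.09 + 0.03) = 43%.

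**Step 3: joint probability.** The six test statistics are treated as multivariate normal, with means set to give the stated powers (2 million draws). For two tests of the same comparison, correlation = shared fraction / √(fraction i × fraction j). With independent markers, levels 1 and 2 give 0.36/√(0.45 × 0.80) = 0.60. Between a monotherapy and a combination test this is multiplied by 1/√(2 × 1.5) = 0.577 for the shared SoC arm. Marker overlap is not in the documents, so it was varied:

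- A: PD-L1 high and TMB high do not overlap, and everyone outside the low-risk group is PD-L1 high.
- B: PD-L1 high and TMB high do not overlap, and all TMB-high patients lie outside the low-risk group.

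Chance of a formal claim (%), Table 5 powers:

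| Overlap | L1 | L2 | L3 | L4 | L5 | L6 |
|---|---|---|---|---|---|---|
| Independent markers | 90.0 | 76.9 | 70.1 | 68.7 | 68.4 | 67.7 |
| Nested (TMB in PD-L1 in low risk) | 90.0 | 78.2 | 72.6 | 71.3 | 70.7 | 69.9 |
| Minimum overlap A | 90.0 | 75.4 | 69.0 | 67.6 | 67.5 | 66.8 |
| Minimum overlap B | 90.0 | 77.6 | 68.3 | 66.8 | 66.8 | 66.2 |

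With the prose powers at levels 3 and 4, level 6 becomes 62.7, 65.1, 61.9 and 60.5% in the same order.

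**Step 4: size of the gap.** Stated power minus the range above, Table 5 powers:

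- Level 2: 81 − (75.4 to 78.2) = 3 to 6 points.
- Level 3: 88 − (68.3 to 72.6) = 15 to 20.
- Level 4: 96 − (66.8 to 71.3) = 25 to 29.
- Level 5: 91 − (66.8 to 70.7) = 20 to 24.
- Level 6: 97 − (66.2 to 69.9) = 27 to 31. With the prose TMB powers it is 97 − (60.5 to 65.1) = 32 to 37.

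**The case against.** The best defence is that power per comparison is a conventional way to report, and that nothing was miscalculated. Each SAP 1.3 paragraph names its own comparison and uses that comparison's hazard ratio. The gate is not hidden: SAP 1.3 refers to the hierarchical procedure just before the powers, section 4 spells out the stopping rule, and Table 5 lists its rows in testing order with 81% in the second. SAP section 4 defines a positive study by level 1 alone.

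Much of this stands. A reader might infer that the 97% is an arithmetic error; Step 1 shows that it is not. Nor do the documents support a reading in which the error rate or the primary power is affected: the sequence controls type I error, and the 90% at level 1 has no gate before it. A reader might also multiply the six powers and quote 54% for level 6 (49% with the prose powers). That treats the tests as independent, although they share patients and a control arm.

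What does not stand is that convention removes the need for a label. The figures follow directly on the hierarchy and are worded as power to show significance, yet neither document calls them stand-alone, and from level 3 on they exceed what the rule allows.

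**Conclusion.** The point holds as one of labelling and omission. The 81% ceiling follows from the SAP's own level-2 power and stopping rule and needs no assumption about overlap. Level 2 itself loses little, at about 75-78% against 81%. The material overstatement is at levels 4-6, by roughly 20-30 points, or more with the prose TMB powers.

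The 66-70% at level 6 (60-65% with the prose powers) takes all six assumed hazard ratios as true together, uses patient shares for the correlations, and depends on overlap that had to be assumed. It is steady over the layouts tried, but the bounds free of any overlap assumption are 43-81% with Table 5 powers. A reader might therefore want one replacement figure per level; the documents do not support that while the overlap is unstated and the TMB powers conflict.

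**What to change.** 1. Reconcile the two sets of TMB powers first (82% or 88% at level 3; 92% or 96% at level 4).
2. Label the Table 5 power column, and the SAP 1.3 paragraphs for levels 2-6, as stand-alone power per comparison that ignores the gate.
3. State in SAP 1.3 that the chance of a formal claim cannot exceed 81% from level 2 on.
4. Add a column to Table 5 for power within the multiple testing procedure, given as a range with its marker-overlap assumption. Blinded prevalence and overlap counts, if available, would narrow it.
5. In Protocol Table 11 a footnote to the second row is enough.

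The cost is wording and one short calculation. Hypotheses, order, alpha, event target and analysis are unchanged; the stated prospects for the later claims become less favourable.
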